5.3 Rationale for the study design

Current Phase IIb Study

The doses selected for the Phase IIb study have been chosen based on the best results seen from previous Phase I human trial studies.

This is a randomised, double-blind, placebo-controlled, single-centre, Phase 2b study of FLU-v administered at Day -43 and Day -22 prior to intranasal challenge at Day 0 with the Influenza A 2009 H1N1 human challenge virus. Subjects will be randomised 1:1:1 to three treatment arms:

- Group 1: adjuvanted placebo on Day -43 and on Day -22
- Group 2: 500 mcg adjuvanted FLU-v vaccine on Day -43 and 1 dose of adjuvanted placebo on Day -22
- Group 3: 500 mcg adjuvanted FLU-v vaccine on Day -43 and on Day -22

A placebo control will be used to establish the frequency and magnitude of changes in endpoints that may occur in the absence of active treatment. Randomisation will be used to minimize bias in the assignment of participants to treatment groups, to increase the likelihood that known and unknown participant attributes (e.g., demographic and baseline characteristics) are evenly balanced across treatment groups, and to enhance the validity of statistical comparisons across treatment groups. Blinded treatment will be used to reduce potential bias during data collection and evaluation of endpoints. Due to the local injection site reactions likely from Montanide ISA-51 adjuvant, masking of syringe barrels is deemed superfluous. However, the blinded study personnel will remain blinded to the presence or absence of FLU-v vaccine.

In this study, the main efficacy comparisons are for each of the FLU-v groups to placebo. The study will also compare the two FLU-v dosing arms but the study will only have power to detect a significant difference in MMID rates between the FLU-v groups and placebo and not against each other.

Assuming significant efficacy of at least one dose of FLU-v against placebo is demonstrated in the current protocol (Part A), when all the primary efficacy endpoint and key safety results are available, the protocol may be amended to include a second part (Part B) which will test the optimal FLU-v dose from Part A (in terms of efficacy and safety) versus current standard of care seasonal influenza vaccine. Details of Part B will be determined and documented in a future protocol amendment following the availability of the unblinded key efficacy and safety results from Part A. Approval will be sought via a substantial amendment from the competent authority before part B can commence

5.3.1 Overall benefit/risk assessment

Based on the available data and proposed safety measures, the overall risk/benefit assessment for this study is considered acceptable.

Influenza (flu) is an infectious disease of birds and mammals caused by an RNA virus of the family Orthomyxoviridae (the influenza viruses). In humans, common symptoms of influenza infection are fever, sore throat, muscle pains, severe headache, coughing, and weakness and fatigue. In more serious cases, influenza causes pneumonia, which can be fatal, particularly in young children and the elderly.

Typically, influenza is transmitted from infected people through the air by coughs or sneezes, creating aerosols containing the virus. Influenza can also be transmitted by saliva, nasal secretions, faeces and blood. Infections occur through contact with these bodily fluids or with contaminated surfaces. Flu viruses can remain infectious for about one week at human body temperature, over 30 days at 0°C (32°F), and indefinitely at very low temperatures. Most influenza strains can be inactivated easily by disinfectants and detergents.

Flu spreads around the world in seasonal epidemics. This was the situation during the influenza pandemic of 1918-19, when a completely new influenza virus subtype (influenza A/H1N1) emerged and spread around the globe in around four to six months. Several waves of infection occurred over two years, killing an estimated 40-50 million people. Since then there have been two subsequent influenza pandemics, in 1957 and 1968. In 2009, the swine flu (H1N1) was the cause of a pandemic that reached a phase 6 pandemic alert and was moderate in severity. Currently available influenza vaccines utilise a Quadrivalent killed vaccine, incorporating two A strains (H1N1 like and H3N2 like) and a two B strains. Whilst these vaccines confer a degree of immunity; antigenic drift, together with the emergence of newer strains, limit their usefulness to a single season, and the need for annual manufacture has considerable impact on cost, as well as the risk that an incorrect prediction of the virus types will lead to an unacceptable level of protection. There is a need for a “universal” vaccine that would be available on an annual basis for winter influenza, but would also have the ability to be rapidly deployed in the face of a pending pandemic, without the need to identify the novel strain and develop a novel vaccine.

PepTcell have developed a novel approach to this problem by developing a vaccination that contains four polypeptides, each of which contains multiple epitopes thought to generate a significant cell-mediated and antibody immune response to the influenza virus, named FLU-

v. Importantly, however, PepTcell have shown that these polypeptide sequences are relatively conserved between different strains and are therefore likely to provide a more consistent immune response, even in the face of a variety of viral strains.

FLU-v has undergone comprehensive testing in a number of non-clinical studies including safety pharmacology, repeat dose toxicology, four-week repeat dose toxicology and local tolerance tests conducted in rats, mice and rabbits. Overall, the vaccine and vaccine/adjuvant combinations were safe and had no significant toxicity at the doses tested. Safety pharmacology studies in rats showed only minor and transient changes in cardiovascular and respiratory parameters that were not considered biologically relevant. In addition, local tolerance of FLU-v administered subcutaneously with or without adjuvant (ISA 51), was assessed in rabbits each receiving a single subcutaneous injection of 502.7 µg FLU-v. Following observation for five days, the animals showed no sign of local reaction to treatment and no clinical signs or treatment-related bodyweight changes during the study period. Subcutaneous injection of FLU-v or FLU-v with adjuvant was well tolerated with no local or systemic sign of reaction to treatment. Although there were some histological findings, these were considered to be due to treatment with adjuvant or were procedural. There were no treatment related findings associated with FLU-v observed in the study. Two Phase I studies have demonstrated good safety, tolerability and good immunological responses in human subjects

In summary, the clinical and non-clinical studies completed with Flu-v suggest that this vaccine has an acceptable safety profile, well tolerated and suitable for ongoing development in human studies. In addition, PepTCells novel approach identifying conserved epitopes of the influenza vaccine differs from approaches used previously. Given these factors and the fact that a vaccination treatment is likely to represent an important option not only for seasonal influenza, but also as an important public health treatment in the event of a pandemic, the potential benefits of this study outweigh the risks.

5.3.1.1 Vulnerable populations

To reduce the risk of passing the Challenge Virus to others, subjects will be asked to avoid contact with vulnerable people for 2 weeks after they leave quarantine. For the purposes of this protocol, a vulnerable individual is a person who:

- Is a child under five years old
- Is elderly (aged 65 years or older)
- Pregnant or breastfeeding women
- Has known immunodeficiency
- Is receiving immunosuppressant medications
- Is undergoing or soon to undergo cancer chemotherapy within 28 days of Viral Challenge
- Has been diagnosed with chronic obstructive pulmonary disease (COPD) or other severe lung or heart disease
- Has received a bone marrow or solid organ transplant.

Should any new information relevant to the subjects' participation in the study and their safety become available, a member of the hVIVO medical staff will notify subjects in a timely manner. If appropriate, subjects will be asked to reconfirm their consent to their participation in the study.

6 STUDY OBJECTIVES

6.1 Primary objective

To determine the effect of FLU-v in reducing the incidence of Mild to Moderate Influenza Disease (MMID) defined as detectable viral shedding plus at least one symptom of influenza

Assuming significant efficacy of at least one dose of FLU-v against placebo is demonstrated in the current protocol (Part A) when all the primary efficacy endpoint and key safety results are available, the protocol may be amended to include a second part (Part B) which will test the optimal FLU-v dose from Part A (in terms of efficacy and safety) versus current standard of care seasonal influenza vaccine. Details of Part B will be determined and documented in a future protocol amendment following the availability of the unblinded key efficacy and safety results from Part A. Approval will be sought via a substantial amendment from the competent authority before part B can commence

6.1.1 Primary endpoint

Incidence of MMID.

6.2 Secondary objectives

To determine the overall effect of FLU-v on measurements of disease severity.

6.2.1 Secondary endpoints

- Viral shedding duration
- Viral shedding quantitation
- Symptom duration
- Total number of symptoms experienced
- Symptom severity score as measured by FLU-PRO Symptom Questionnaire
- Incidence of vaccine related adverse events (diary card for 21 days after each vaccine)

6.3 Exploratory objectives

To explore the immunological responses to FLU-v

6.3.1 Exploratory endpoints

- Immunogenicity of FLU-v as measured by
 - B-cell and T-cell responses to FLU-v both after vaccination as well as influenza challenge
 - Immunophenotyping
- Broadness of protection as measured by culturing PBMCs pre-influenza virus inoculation in study with PBMCs (same subject) infected with influenza and assess killing of infected cells by PBMCs from vaccinated subjects and use sera containing

non-neutralising antibodies and test killing of human influenza infected cells by complement activation or ADCC assays.

Exploratory endpoints may be reported separately from the clinical study report (CSR).

6.4 Safety objectives

To determine the safety and tolerability of FLU-v after vaccination in healthy subjects subsequently challenged with Influenza A 2009 H1N1 human challenge virus

6.4.1 Safety endpoints

- Incidence of treatment-emergent AEs (TEAE), severity, seriousness and causality
- Absolute values and change from baseline in routine clinical and laboratory parameters
- Vaccine Related Physical examination findings
- Concomitant medications.

7 STUDY POPULATION

Participants will be carefully selected using the inclusion and exclusion criteria described here to select the optimum participants for completing the study objectives and minimize the risk of adverse events (AEs).

7.1 Number of subjects

Up to 123 subjects will be inoculated with the influenza challenge virus at a dose of 10^7 TCID50 after being randomised 1:1:1, and dosed with FLU-v 1 dose plus placebo, 2 doses, or placebo

7.2 Inclusion criteria

Each potential subject must satisfy all of the following criteria to be enrolled in the study.

NO	INCLUSION CRITERIA
1	Healthy males and females aged ≥ 18 and ≤ 55 years of age at the point of enrolment.
2	Willingness to remain in isolation for the duration of viral shedding and to comply with all study requirements.
3	
The following criteria are applicable to subjects in a heterosexual relationship and female subjects in a same sex relationship (i.e., the criteria do not apply to male subjects in a same sex relationship):
 
- True abstinence- when this is in line with the preferred and usual lifestyle of the subject. (Periodic abstinence [e.g. calendar, ovulation, symptothermal, post-ovulation methods] and withdrawal are not acceptable methods of contraception). 
Or
 
- Two forms of effective contraceptive methods among (between) the couple, which are defined as:
o For males: condom with spermicidal foam/gel/film/cream, sterilisation (with the appropriate post-vasectomy documentation of the absence of sperm in the ejaculate. This applies only to males participating in the study).o For females:
▪ Women no longer of child bearing potential (post-menopausal females are defined as having a history of amenorrhea for at least 2 years, otherwise they should have documented status as being surgically sterile or post hysterectomy. The latter applies only to females participating in the study).

NO	INCLUSION CRITERIA
	
 ▪ If of childbearing potential, then acceptable forms of contraception include: 
 ▪ Established (a minimum of 2 weeks prior to admission) use of oral, injected or implanted hormonal methods of contraception. 
 • Placement of an intrauterine device (IUD) or intrauterine system (IUS). • Barrier methods of contraception or occlusive cap (diaphragm or cervical/vault caps), both with one of the following - spermicidal foam/gel/film/cream/suppository. ○ The longevity of contraception is as follows: 
 ▪ Males: 
 • Comply with agreed contraception at entry to quarantine, and continuing until 90 days after the date of viral challenge/last dosing with IMP (whichever occurs last). • Must not donate sperm following discharge from quarantine until 90 days after the date of viral challenge/last dosing with IMP (whichever occurs last). ▪ Females: 
If of childbearing potential must have a negative pregnancy test at screening and just prior to the date of Viral Challenge, and must be using contraception consisting of two forms of birth control (one of which must be a barrier method) starting from at least 2 weeks prior to the first vaccination and continuing until 90 days after the date of Viral Challenge/last dosing with IMP (whichever occurs last).

4	Willing to have samples stored for future research.
5	Sero-suitable to the study challenge virus within 90 days of Day 0.
6	Agrees to abstain from alcohol intake 24 hours before admission on Day -2 or Day -1 and all other outpatient visits.
7	Agrees to not use prescription or over-the-counter medications (including aspirin, decongestants, antihistamines, and other NSAIDs), and herbal medication (including, but not limited to, Vitamin C, Vitamin D, immune booster products, herbal tea, St. John's Wort), within 14 days prior to study vaccine administration through the final follow-up visit, unless approved by the investigator and sponsor medical monitor.
8	An informed consent document signed and dated by the subject and the Investigator or delegate.

NO	INCLUSION CRITERIA
9	A history of childhood asthma before the age of 12 years is acceptable provided the subject is asymptomatic without treatment. Subjects with a single episode of wheezing (lasting less than 2 weeks) after the age of 12 years can be included at the Investigator's discretion provided the episode was more than 1 year ago and did not require a hospital admission and/or oral/intravenous steroids.
10	In good health with no history of major medical conditions that will interfere with subject safety, as defined by medical history, physical examination, and routine laboratory tests and determined by the Investigator at a screening evaluation. 
• A subject with a history of Herpes type 1 or 2 infection may be included if there are no active lesions present and the subject is not taking active medication.• A subject with or without any evidence of atopy including any history of allergic rhinitis, dermatitis, and conjunctivitis will be included as long as they do not conflict with exclusion criteria. Mild to moderate arthritis of non-inflammatory origin may be allowed if the subject is not at risk from relative immobility in the Quarantine Unit and does not require regular medication.
11	A documented medical history for a minimum of the last 2 years prior to inoculation.

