FLU-v-002 was a single-centre, randomised double-blind, placebo-controlled, Phase Ib trial to evaluate the safety, tolerability and protective efficacy of the influenza vaccine candidate, FLU-v, in an influenza challenge model. 32 subjects were vaccinated, 28 were quarantined and 27 completed the study. 16 subjects FLU-v 500 μ g + adjuvant and the other 16 received placebo + adjuvant. Subjects were healthy males aged 18 to 45 years, who had not had seasonal influenza vaccination since 2006 or a known influenza infection in the 12 months prior to study entry, who were serosusceptible to Influenza A/Wisconsin/67/2005 (H3N2) virus at screening, and in good health as determined by past medical history, physical examination, vital signs, electrocardiogram (ECG), and laboratory tests at screening.

Efficacy

The study demonstrated similar good immune responses to the previous Phase I study following FLU-v treatment (see Section 6.3.2 in the IB v4.0 7th June 2016). The dose of Challenge Virus used in the study was intended to cause mild symptoms in volunteers, and an attack rate of approximately 70% to 80% in the placebo group, which was not achieved.

It is possible that in this study, the low rates of infectivity in the placebo group and the resulting apparent lack of efficacy of FLU-v may have been related to pre-existing multi-strain (i.e., heterologous) cellular immunity arising from previous asymptomatic exposure of the population to viral infection during a recent Influenza pandemic between June 2009 and February 2010. In addition, pre-existing T cells responding to Influenza internal proteins may have been associated with lower virus shedding and a less severe illness.

As a result of these potential unforeseen circumstances, there was no statistical evidence that FLU-v conferred clinical protection to subjects or reduced illness subsequent to being challenged with intranasal Influenza A/Wisconsin/67/2005 (H3N2). However, when looking at the subjects in each group that did not have a pre-existing T cell response to the challenge

strain, the subjects in the control group were more symptomatic and 'ill' compared to the subjects in the vaccinated group who did not become significantly symptomatic. (see Section page 12 in the IB v4.0 7th June 2016).

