8.5 Contraception

Male and female subjects of childbearing potential who engage in heterosexual intercourse must agree to utilize protocol-recommended methods of contraception. The required contraceptive measures are outlined in the study eligibility criteria (Section 7.2).

Postmenopausal women (no spontaneous menses for at least 2 years), women with surgical sterilisation (documented GP evidence of a total hysterectomy, bilateral oophorectomy, bilateral tubal ligation/bilateral tubal clips without reversal operation), and women who are otherwise incapable of becoming pregnant must use a condom when having heterosexual intercourse from 2 weeks prior to entry to quarantine and continuing until 90 days after the date of Viral Challenge / last dosing with IMP (whichever occurs last).

Study approved contraceptive methods

Established use of oral, injected or implanted hormonal methods of contraception.

Placement of an intrauterine device or intrauterine system.

Barrier methods of contraception: Condom or diaphragm with spermicidal foam/gel/film/cream/suppository.

Male sterilisation (with the appropriate post-vasectomy documentation of the absence of sperm in the ejaculate). [For female subjects on the study, the vasectomized male partner should be the sole partner for that subject].

True abstinence: When this is in line with the preferred and usual lifestyle of the subject. Periodic abstinence (e.g., calendar, ovulation, symptothermal, post-ovulation methods) and withdrawal are not acceptable methods of contraception.

Subjects should be advised that a male and female condom should not be used together due to risk of breakage or damage caused by latex friction.

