9.2 Vaccination Phase

9.2.1 Visit 2 - Day -43

The first vaccine or placebo administration will take place on Day -43, 43 days prior to virus challenge. Study procedures will be conducted as detailed on the Time and Events, table 9.2

Once it is determined that the participant still meets Inclusion/Exclusion criteria for the research study, participants will receive the first of two injections of FLU-v 500mcg+adjuvant 2 doses, FLU-v 500mcg 1 dose + 1 dose placebo , or 2 doses of placebo. The study team will thoroughly discuss the consent with the volunteer. The study team will issue and explain the completion of self-reported adverse events in a 21-day diary card. This diary card will be used to record vaccine-related local and systemic events post first vaccination.

9.2.2 Visit 3 - Day -22 (minimum 21 days post first vaccination +7 days)

The second study drug administration will take place if the participant continues to meet all inclusion and none of the exclusion criteria. Study procedures will be conducted as detailed on the Time and Events schedule

The study team will issue and explain the completion of self-reported adverse events in a 21-day diary card. This diary card will be used to record vaccine-related local and systemic events post second vaccination.

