9.3 Quarantine and Challenge

9.3.1 Visit 4 - Admission (Day -2 or Day -1 up to 40 days post second vaccination)

Subjects will be admitted to the Quarantine unit on day -2 or day -1 (minimum 20 days post second vaccination). If subject is not available to attend admission on the Day -2/Day -1 due date, the visit can be scheduled up to 40 days post second vaccination.

The admission procedures/assessments and testing will be performed after admission and before challenge virus administration. Study procedures will be conducted as detailed on the Time and Events schedule

As determined by the PI, results of standard procedures performed in the process of admission to the Quarantine unit may be used to determine suitability, including but not limited to vital signs, height, weight, etc. They can also be used to extend eligibility beyond 90 days from

screening if the participant has been vaccinated but his admission has fallen out of the 90 days window. A Viral Challenge serology test can be repeated if required before Quarantine if the participant has been vaccinated but the admission date has fallen out of the 90 days window. However, the serology test and result must be dated within 90 days of Day 0.

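### Criterion 3 starts men's contraception only after both vaccine doses, and its two timing lines for women of childbearing potential name dates 41 to 42 days apart

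*Protocol*

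**What the plan says.** Protocol section 7.2, criterion 3, gives the timing of contraception in several places.

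- **Women of childbearing potential, list of acceptable methods:** "Established (a minimum of 2 weeks prior to admission) use of oral, injected or implanted hormonal methods of contraception".
- **Women of childbearing potential, duration of contraception:** two methods, one of them a barrier, "starting from at least 2 weeks prior to the first vaccination and continuing until 90 days" after challenge or the last IMP dose, whichever is later.
- **Men, duration of contraception:** "Comply with agreed contraception at entry to quarantine", with the same 90-day end point. A separate line bars sperm donation from discharge from quarantine.

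Section 8.5 refers back to section 7.2 for the required measures and gives men no earlier start. It lists hormonal methods again, without a lead time. Women who cannot become pregnant "must use a condom when having heterosexual intercourse from 2 weeks prior to entry to quarantine".

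On the calendar, section 9.2.1 states: "The first vaccine or placebo administration will take place on Day -43, 43 days prior to virus challenge". The second dose is on Day -22 (section 9.2.2). Quarantine admission is on Day -2 or Day -1 (section 9.3.1).

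**The concern.** The protocol itself treats IMP as an exposure that matters for contraception. The end point for both sexes refers to the last IMP dose as well as to challenge, and the women's duration line starts before the first vaccination. The men's start is tied to quarantine alone, which comes about three weeks after the second dose. A start that ignores dosing sits beside an end that counts it, and no reason is given.

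For women of childbearing potential, one criterion gives two different lead times. A screener has to work out which one governs. Section 18.3.1 bars waivers, so the wording decides enrolment.

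What is at stake is the safety of participants and partners, and consistent eligibility decisions. Sample size, error rate and the endpoint analyses are not affected.

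**Working it through.** **Inputs**

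- Dose 1: Day -43 (section 9.2.1).
- Dose 2: Day -22, at least 21 days after dose 1 with a window of 7 further days, so 21 to 28 days (section 9.2.2).
- Admission: Day -2 or -1, at least 20 and at most 40 days after dose 2 (section 9.3.1).
- In the criteria, admission means quarantine admission: criterion 6 ties the word to Day -2 or Day -1.

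**The plan's own intervals**

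- Dose 1 to dose 2: -22 - (-43) = 21 days, which matches the stated minimum of 21.
- Dose 2 to admission: -2 - (-22) = 20 days, or -1 - (-22) = 21 days. This matches the stated minimum of 20.

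**Men: delay from dose to start of the rule**

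| From | Nominal calendar | Longest with visit windows |
|---|---|---|
| Dose 1 | -2 - (-43) = 41, or -1 - (-43) = 42 days | 28 + 40 = 68 days |
| Dose 2 | 20 or 21 days | 40 days |

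The sperm-donation restriction begins later still, at discharge. No line in section 7.2 or 8.5 gives men an earlier start.

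**Women of childbearing potential: the two lines side by side**

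- Duration line: -43 - 14 = Day -57.
- Hormonal-method line, latest start: -2 - 14 = Day -16, or -1 - 14 = Day -15.
- Difference: -16 - (-57) = 41, or -15 - (-57) = 42 days. With the full windows it equals the longest gap from dose 1 to admission, 68 days.
- A start on Day -16 or -15 falls 27 or 28 days after dose 1 and 6 or 7 days after dose 2. With windows this is up to 68 - 14 = 54 and 40 - 14 = 26 days.

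**Example.** A woman starts hormonal contraception on Day -50 and relies on it as one of her two methods.

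- Hormonal-method line: -2 - (-50) = 48 days (49 if admitted on Day -1) before admission. She can meet the 14-day requirement.
- Duration line: -43 - (-50) = 7 days before first vaccination. She fails the 14-day requirement.

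**Which line governs for women.** Section 7.2 requires every criterion to be satisfied, and both lines can be satisfied together. The duration line asks for the earlier date, so it binds. No such reasoning helps for men, because there is no second line to apply.

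**The case against.** The strongest reply concerns women. The hormonal line sits in a list of methods, and the duration line says when contraception must be in place. With all criteria required and waivers barred, only the stricter reading is open. That stands. A reader might infer that women can be dosed with no contraception requirement in force, but that follows only if the duration line is ignored. The protocol also requires pregnancy tests at screening and on Days -43, -22 and -2, and exclusion 25 removes anyone with a positive test before first dosing. These tests do not set a start for contraception, and they do nothing for the partners of male subjects.

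Three further inferences are tempting and are not supported.

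- **Opposite decisions on a woman who starts hormonal contraception four weeks before admission.** That is Day -30 or -29, after the eligibility check on Day -43, so she has no established use to judge at that check.
- **A conception risk from the condom rule in section 8.5.** That rule covers women who cannot conceive.
- **First exposure of women to FLU-v.** Section 5.2.3.1 describes two completed studies, both in men; of the second it says "Subjects were healthy males aged 18 to 45 years". The documents do not say whether any other FLU-v study exists or whom it enrolled, so this is inference only.

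On men, the reply is that different start points by sex may be deliberate, since no passage says that the male and female rules share one purpose. It is fair that the text does not prove a mistake. But the protocol gives no reason for the difference, and the men's own end point counts from the last IMP dose. Clarification is needed either way.

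**Conclusion.** The point holds in two parts of unequal weight.

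- **Men:** as written, no contraception requirement is in force at either IMP dose. The rule begins 41 to 42 days after dose 1 and 20 to 21 days after dose 2, and up to 68 and 40 days with the windows.
- **Women of childbearing potential:** two lines of one criterion differ by 41 to 42 days, and by up to 68 with the windows. The duration line binds, so this is an inconsistency in wording and not an unprotected gap.

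The figures rest on admission meaning quarantine admission. The upper values assume that both visit windows are used in full. The documents establish that the lines disagree and do not fit the dosing schedule; they do not establish which start point is right.

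**What to change.** The sponsor should reconcile, within criterion 3, the male duration line, the sperm-donation line and the hormonal-method line with the female duration line. All of them should then be reconciled with the dosing schedule (Days -43 and -22) and with section 8.5. If a different start for men is intended, the protocol should say so and give the reason. The reconciled wording should be carried into the consent form.

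The choice of start point belongs to the sponsor and the regulator, and none is proposed here. The cost is amendment and consent-form wording only.
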